### ***Statistical Analysis***

The distributions of baseline patient characteristics and outcome variables will be compared between two groups using chi-square tests or Fisher's exact test for categorical variables and either t tests or Wilcoxon rank sum tests for continuous variables, as appropriate. For time to event data, Kaplan-Meier method and log-rank test will be applied for group comparisons. Multivariable logistic regression, simple linear regression, or Cox proportional hazards regression analyses will be used to identify potential influential factors of outcomes of interest. A two-sided significance level of 0.05 was used to define statistically significant difference. All the statistical analyses will be conducted using Statistics Analysis System (SAS), Version 9.4 (SAS Institute Inc., Cary, NC, USA).

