### 4. Study Design

We will use the design of factorial parallel randomized controlled trial to conduct these two studies in the same patient group. A computer-generated list of randomizations (Research Randomizer, [www.randomizer.org](http://www.randomizer.org)) will be used for these group allocations. We will use stratified randomization method to ensure random allocations of these two treatments (spectral entropy and ProAQT goal-directed therapy) in all patients. Allocation will be concealed with sequentially numbered sealed opaque envelopes. The principal investigator will open the respective concealed envelope containing the patient allocation to the treatment arm on the day of surgery immediately before induction of anesthesia. In this trial, we will conform to the recommendations in the Consolidated Standards of Reporting Trials (CONSORT) statement. In addition, we will follow the principle of intention-to-treat in our analyses of the trial results.

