In the M-Entropy group, dosage of volatile anesthetics will be adjusted to achieve the response and state entropy values between 40 and 60 from the start of anesthesia to the end of surgery. In the control group, dosage of volatile anesthetics will be titrated according to clinical judgment. This will be to maintain mean arterial pressure and heart rate within 20% range of the baseline. In case of signs of inadequate anesthesia (e.g. movement, cough and swallowing), anesthetic dose will be increased. M-Entropy monitoring will be continued in the control group, but the entropy number and EEG waveform will be concealed from the anesthetist in charge. Entropy values, hemodynamic, and expiratory gas data will be recorded in 5-min intervals. In all patients, cessation of general anesthesia will be timed to facilitate early awakening after wound closure. After reversal of the neuromuscular blocking agent and response to verbal command, all subjects will be extubated at the operating room and then transferred to the postanesthetic care unit. In the postoperative period, surgeons, medical and nursing staff at the postanesthetic care unit will be blinded to group allocation.

Primary outcome is time to spontaneous eye opening. Secondary outcomes include time to tracheal extubation, time to orientation in time and place, time to leave operating room, and events of emergence agitation, postoperative delirium, and intraoperative recall or awareness. We will use the Richmond Agitation-Sedation Scale to evaluate the level of agitation and sedation promptly after extubation. Events of delirium will be evaluated using the Confusion Assessment Method at the postanesthetic care unit 30 minutes after tracheal extubation. An independent adjudicator blinded to the group allocation will measure all the outcomes.

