The primary outcome is in-hospital postoperative pulmonary complication, including atelectasis, pleural effusion, pneumonia, empyema, pulmonary embolism, re-operation, and respiratory failure. The diagnosis of atelectasis and pleural effusion will be made based on routinely performed chest radiographs on postoperative days 1 and 3. Pneumonia will be diagnosed if a patient presents with fever, leukocytosis and new infiltrates on chest radiography. Pleural empyema and pulmonary embolism will be confirmed by spiral computed tomography scan. Respiratory failure is defined as described. Secondary outcomes include relative change of PaO2/FiO2, PaO2/FiO2 values after induction of anesthesia and at the end of surgery, acute kidney injury (defined by Acute Kidney Injury Network Criteria), cardiac complications (myocardial infarction diagnosed by electrocardiogram and troponin T serum concentration; newly developed atrial fibrillation), clinically relevant hypotensive episodes (decrease in mean arterial pressure > 20% for more than 15 min requiring vasopressors), newly developed stroke, and length of hospital stay. All outcomes will be determined again 30 days after surgery and documented by research staff blinded to group allocation.

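### No prespecified covariate-adjusted analysis exists for either primary outcome: the named comparisons are unadjusted and the regressions are given only a factor-finding purpose

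*Combined protocol and SAP*

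**What the plan says.** Everything on analysis is in the Statistical Analysis paragraph at the end of section 5.

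- Baseline data and outcomes share one sentence and one set of tests: "The distributions of baseline patient characteristics and outcome variables will be compared between two groups using chi-square tests or Fisher's exact test", followed by t or Wilcoxon tests for continuous variables.
- For times to event: "For time to event data, Kaplan-Meier method and log-rank test will be applied for group comparisons".
- On regression: "Multivariable logistic regression, simple linear regression, or Cox proportional hazards regression analyses will be used to identify potential influential factors of outcomes of interest".
- One significance level is given: "A two-sided significance level of 0.05 was used to define statistically significant difference".

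The M-Entropy part of section 5 states: "Primary outcome is time to spontaneous eye opening". The ProAQT part states: "The primary outcome is in-hospital postoperative pulmonary complication, including atelectasis, pleural effusion, pneumonia, empyema, pulmonary embolism, re-operation, and respiratory failure".

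Section 4 (Study Design) describes allocation as stratified: "We will use stratified randomization method to ensure random allocations of these two treatments (spectral entropy and ProAQT goal-directed therapy) in all patients". It names no baseline stratification factor.

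**The concern.** Every group comparison that the plan names is a two-group test without covariates, and this covers both primary outcomes. The regression sentence does not fill the gap. It lists no covariates, does not say that the treatment terms enter the models, and does not say that any model supplies the primary estimate. For continuous outcomes the only regression named is the simple linear kind. Read literally, that has one predictor and cannot hold treatment and a covariate together.

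Two things are at stake. If baseline variables predict the outcome, an unadjusted comparison uses the patients less efficiently than it could. And because the role of the regressions is open, an analyst could choose the covariates, and choose between an adjusted and an unadjusted result, after seeing the data.

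**Working it through.** The documents give no sample size, power, event rate, standard deviation or list of baseline variables, so there is no figure of the plan's own to reproduce. The inputs below are assumptions, except the two-sided 0.05 level.

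**1. Which analysis applies to each primary outcome**

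| Primary outcome | Named group comparison | Possible regression | Stated role of regression |
|---|---|---|---|
| Time to spontaneous eye opening | Log-rank, or t/Wilcoxon (not settled) | Cox, or simple linear | Finding influential factors |
| Pulmonary complication | Chi-square or Fisher | Multivariable logistic | Finding influential factors |

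Neither row contains an adjusted treatment estimate fixed in advance.

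**2. Overall error of the unadjusted test.** Let ρ be the correlation between one baseline covariate and the outcome. In a simulation of 2,000,000 draws under no treatment effect, never adjusting gave 5.0% error at ρ = 0.3 and at ρ = 0.5, and always adjusting also gave 5.0%. Adjusting only when the baseline test was significant gave 4.8% (ρ = 0.3) and 4.3% (ρ = 0.5).

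**3. Error conditional on a given imbalance.** If the covariate differs between arms by a standardised z, the unadjusted statistic is distributed as N(ρz, 1 − ρ²), and the error is P(|Z| > 1.96).

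| Baseline z (p) | ρ = 0.1 | ρ = 0.3 | ρ = 0.5 |
|---|---|---|---|
| 1.5 (0.13) | 5.1% | 6.2% | 8.2% |
| 1.9 (0.06) | 5.3% | 7.7% | 12.2% |

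For ρ = 0.5 and z = 1.9 the mean is 0.95 and the SD √0.75 = 0.866. The upper tail starts at (1.96 − 0.95)/0.866 = 1.17, and the two tails together give 12.2%. A non-significant baseline test therefore does not show that an imbalance is harmless when the covariate is strong. For a weak covariate it hardly matters.

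**4. Gain for a continuous outcome in a linear model.** The variance of the treatment effect is multiplied by 1 − R², which is equivalent to 1/(1 − R²) times as many patients. Starting from an assumed 80%, power becomes Φ((1.96 + 0.84)/√(1 − R²) − 1.96).

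| R² | Equivalent extra patients | Power |
|---|---|---|
| 0 | 0% | 80% |
| 0.05 | 1/0.95 − 1 = 5% | 82% |
| 0.10 | 1/0.90 − 1 = 11% | 84% |
| 0.20 | 1/0.80 − 1 = 25% | 88% |
| 0.30 | 1/0.70 − 1 = 43% | 92% |

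**5. Gain for the binary outcome, by simulation of logistic models.** Assumed: control risk 30%, 120 per arm, conditional odds ratio 0.42, 3,000 runs.

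| Covariate c-statistic | Power unadjusted | Power adjusted | Gain (points) |
|---|---|---|---|
| 0.58 | 76.7% | 77.0% | 0.3 |
| 0.64 | 74.2% | 76.7% | 2.5 |
| 0.70 | 70.6% | 75.1% | 4.5 |
| 0.76 | 65.1% | 73.2% | 8.1 |

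A separate simulation (200 patients in total, log odds ratio −0.85, 1,500 runs) moved power from 75% to 77% with a covariate log odds ratio of 0.5 per SD, and from 61% to 70% with 1.0 per SD. Other runs on similar inputs put the gain for a strong covariate at about 10 points, hence the overall range of about 0 to 10.

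**The case against.** An unadjusted primary comparison in a randomised trial is a legitimate choice, and step 2 confirms that it keeps its level. The size of any gain depends wholly on covariates that the documents do not describe. Both points stand, and they limit this to efficiency and prespecification.

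Four stronger readings are tempting, and the documents do not support them.

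- **That baseline data are never used for adjustment.** Multivariable logistic and Cox models of the outcomes are planned, and nothing bars treatment and baseline terms from them. What is missing is their specification and status.
- **That the planned tests inflate false positives.** The 8.2% and 12.2% in step 3 are conditional on a chosen imbalance and a strong covariate. The overall rate is 5%.
- **That baseline p-values will decide what is adjusted.** The plan states no use for them. Even that rule gave error below 5% in step 2. The simulation covers one fixed rule with one covariate; choosing among results after seeing them was not simulated.
- **That baseline testing itself damages the results.** Allocation uses "A computer-generated list of randomizations", so among all randomised patients any baseline difference is chance and such a test answers no useful question. Dropping the p-values is good reporting practice but changes no result. Section 3 also lists exclusions that can arise after allocation (blood loss, transfusion, transfer for ventilation). If those patients were dropped, the groups would no longer be purely as randomised, and baseline tests would not repair that.

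The simple linear regression wording may be loose drafting. It does not touch the binary primary outcome, and it reaches eye opening only if that is analysed as a continuous variable.

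**Conclusion.** The point holds as a gap in efficiency and prespecification. Both primary outcomes have only unadjusted comparisons, and no covariate-adjusted primary analysis is fixed in advance. The primary tests are not invalid.

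The loss cannot be derived from the documents. It is 5% to 43% in equivalent patients for a continuous outcome if covariates explain 5% to 30% of the variance, and nothing if they explain none. For the binary outcome it is about 0 to 10 power points, under an assumed event risk near 30%, 100 to 120 patients per arm and an odds ratio of about 0.42. The continuous-outcome formula does not carry over to logistic or Cox models, where the gain appears as power for a conditional effect and not as a smaller standard error. Nothing in the documents shows how prognostic the available covariates are. The change is worth making because it costs little and also settles which result is primary.

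**What to change.** In the Statistical Analysis section:

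1. For each primary outcome, name one model that gives the treatment effect with a 95% CI, and state that it is primary. Use logistic regression for pulmonary complication. For eye opening use Cox regression or linear regression on log time, and say which.
2. Include in each model the other factorial treatment, any stratification factor used, and a short list of baseline covariates. Choose these for prognosis, fix them before unblinding, and keep them whatever the observed balance. Age and NYHA class are candidates, since section 3 already needs both for screening.
3. Label the adjusted odds or hazard ratio as conditional on the covariates. The unadjusted comparison can be kept as a supporting analysis.
4. Replace simple with multiple linear regression, so that continuous outcomes can be adjusted as well.
5. Describe baseline characteristics by arm without p-values.

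The cost is revised wording and a little more analysis work. No new patients are needed, nor new data if the covariates are ones already collected. The one drawback is that a conditional ratio needs more care to interpret than a crude one.

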## 1. Introduction

Patients undergoing thoracotomy in thoracic surgery are prone to have complications of delayed recovery from general anesthesia and perioperative instable hemodynamics due to the relatively invasive procedures and patient's underlying morbidity. Therefore, intraoperative monitoring and corresponding management are of great importance to prevent relevant complications in thoracic surgery. This study aims to investigate the clinical benefits of two intraoperative monitoring techniques in patients undergoing thoracotomy surgery, including depth of anesthesia and minimally invasive cardiac output monitoring. First, M-Entropy system will be used to measure the depth of anesthesia and be evaluated regarding the effect of spectral entropy guidance on postoperative recovery. Second, we will apply ProAQT device in guiding goal-directed hemodynamic therapy and assess its impact on occurrence of postoperative pulmonary complications and recovery. In this study, we will conduct a factorial parallel randomized controlled trial and use the method of stratified randomization to evaluate both two monitoring technologies in the same patient group. The results of this study will provide important evidence and clinical implication for precision anesthesia and enhanced recovery after surgery (ERAS) protocol in thoracic surgery.

This study aims to investigate the clinical benefits of two intraoperative monitoring techniques in patients undergoing thoracotomy surgery, including M-Entropy system and ProAQT sensor, as follows:

- 1) To evaluate the effect of M-Entropy guidance on the emergence from anesthesia and risk of postoperative delirium.
- 2) To apply ProAQT in guiding goal-directed hemodynamic therapy and assess its impact on postoperative pulmonary complications and recovery.

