## 2. Background

Thoracic anesthesia comprises a wide variety of diagnostic and therapeutic procedures involving the lungs, airways, and hemodynamic changes. The procedure of thoracotomy inevitably causes pneumothorax, which results in multiple physiology derangements, including ventilation-perfusion mismatch and hypoxia. Furthermore, one-lung ventilation (OLV) is commonly used to facilitate the visualization and surgical manipulation in video-assisted thoracotomy. However, OLV may also cause profound hemodynamic changes, including lung collapse, barotrauma and severe hypotension. The hemodynamic instability may further increase the risk of inadequate depth of anesthesia and thereafter its related complications, such as intraoperative awareness, post-traumatic stress disorder and cognitive dysfunction. Therefore, intraoperative monitoring and corresponding management are of great importance to prevent relevant complications in thoracic surgery.

Because of the advances in monitoring technology in recent decades, the risk of mortality and morbidity of anesthetic practices has significantly declined. Among the newly-introduced technologies, electroencephalography (EEG)-based monitoring of anesthesia depth and indirect cardiac output monitoring are useful and minimally invasive in optimizing the anesthetic patients' intraoperative hypnotic, cardiac output, and intravascular volume status. However, there is sparse evidence regarding the effectiveness of the use of these two monitoring in guiding thoracic anesthesia. Accordingly, this study aims to investigate the effect of guidance of spectral

entropy and indirect cardiac output monitoring on the recovery from anesthesia and postoperative outcomes in patients undergoing thoracotomy.

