### **The effect of application of ProAQT in guiding goal-directed hemodynamic therapy on postoperative recovery: A single-blind randomized controlled trial**

In both groups, intraoperative maintenance rate of crystalloid fluids is  $3 \text{ ml}\cdot\text{kg}^{-1}\cdot\text{hr}^{-1}$ . ProAQT-derived hemodynamic data are acquired at three time periods: before surgical incision, during OLV and at the end of surgery. Subjects randomized to the GDT group will be managed according to the ERAS algorithm utilizing ProAQT variables (mean arterial pressure, stroke volume variation and cardiac index) If stroke volume variation is  $\geq 10\%$ , a bolus of 150 ml of crystalloid fluid will be given until the stroke volume variation is  $< 10\%$ . If mean arterial pressure is  $< 70 \text{ mmHg}$  and/or cardiac index  $< 2.5 \text{ l}\cdot\text{min}^{-1}\cdot\text{m}^{-2}$  despite the stroke volume variation of  $< 10\%$  following fluid challenge, single or consecutive boluses of ephedrine 4 mg and/or continuous intravenous infusion of norepinephrine  $2\text{--}10 \text{ }\mu\text{g}\cdot\text{min}^{-1}$  will be administered. (Figure 1)

[figure not shown]

Figure 1: Goal-directed hemodynamic algorithm to guide intraoperative fluid therapy and the use of vasopressor and inotropic therapy in the goal-directed therapy group

Subjects allocated to the control group are hemodynamically managed as follows. Isolated hypotension (defined as 20% decrease in mean arterial pressure below baseline or < 60 mmHg) is treated by a continuous intravenous infusion of norepinephrine 2–10  $\mu\text{g}\cdot\text{min}^{-1}$ . If hypotension persists, repeat boluses of ephedrine 4 mg will be administered until mean arterial pressure is > 60 mmHg. If hypotension is accompanied by signs of hypovolemia (defined as urine output < 0.5  $\text{ml}\cdot\text{kg}^{-1}\cdot\text{hr}^{-1}$  and/or an increase in heart rate > 20% above baseline), crystalloid fluid will be administered until urine output and/or heart rate are normalized. Colloids are administered only when hypotension develops during acute hemorrhage. If hypotension persists despite volume challenges, norepinephrine will be administered. In both groups, fluid and inotrope or

vasopressor responsiveness and hemodynamic variables will be evaluated each 15 min, and more frequently in case of hemodynamic instability. ProAQT variables will be recorded every 15 min.

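### Every patient is randomised on two factors, but the analysis plan does not specify stratifying or adjusting each comparison for the other factor, and plans no four-cell results or interaction estimate

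*Combined protocol and SAP*

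**What the plan says.** Section 4 (Study Design) sets a factorial trial: "We will use the design of factorial parallel randomized controlled trial to conduct these two studies in the same patient group". On allocation it adds: "We will use stratified randomization method to ensure random allocations of these two treatments". Section 1 (Introduction) also ties stratified randomisation to the wish to "evaluate both two monitoring technologies in the same patient group". Neither section names the strata or gives an allocation ratio.

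Section 5 (Study Methods) then describes each factor as a separate two-group, single-blind trial with its own primary outcome: time to spontaneous eye opening for M-Entropy, and in-hospital pulmonary complications for ProAQT.

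The Statistical Analysis section is the whole analysis plan. Baseline characteristics and outcomes "will be compared between two groups using chi-square tests" or Fisher's exact test, or t or Wilcoxon tests. Time-to-event data get Kaplan-Meier curves and a log-rank test. Multivariable logistic, simple linear or Cox regression is planned to look for factors that influence the outcomes, with no covariates listed. The significance level is two-sided 0.05.

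**The concern.** Two randomised factors give four treatment groups, yet the planned main tests compare two groups at a time and none is described as stratified. Two things are lost.

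- **Efficiency.** If the other monitor affects the outcome, its effect stays in the residual variation of the two-group comparison. The reported standard error is then larger than it need be.
- **Interpretation.** Each marginal comparison estimates a monitor's effect averaged over use and non-use of the other. That answers the two stated aims. It does not show whether the average is a fair summary for patients managed with one monitor or with both, although the randomised groups needed to look at this already exist.

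An interaction is possible because the two interventions share a control variable. In the entropy control arm, anaesthetic is titrated on clinical judgement: "This will be to maintain mean arterial pressure and heart rate within 20% range of the baseline". The goal-directed arm is managed by an algorithm "utilizing ProAQT variables (mean arterial pressure, stroke volume variation and cardiac index", and the ProAQT control arm treats "Isolated hypotension (defined as 20% decrease in mean arterial pressure below baseline or < 60 mmHg". Mean arterial pressure therefore drives anaesthetic titration under one factor and vasopressor use under the other.

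**Working it through.** The documents as supplied give no sample size, event risk, SD or effect size, so there is no figure of the plan's to reproduce. Every input below is an assumption, shown over a range. Cells are taken as balanced.

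**1. What the plan specifies**

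| Feature | Where it might appear | Found? |
|---|---|---|
| Other factor as stratum in the main tests | Statistical Analysis | No |
| Other factor as model term | Statistical Analysis, regressions | Neither named nor excluded in the multivariable models; simple linear regression has one predictor |
| Stratification variables carried into the analysis | Introduction; Study Design; Statistical Analysis | Stratification mentioned in the first two, strata unnamed; absent from the third |
| Four-cell results | Anywhere | No |
| Interaction estimate, or a stated no-interaction assumption | Anywhere | No |

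**2. Standard error when the other factor is ignored (continuous outcome)**

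Let the within-cell SD be 1 and let the other monitor shift the mean by d SD. Within each arm of the tested factor, half the patients have the shift, which adds d²/4 to the variance. So reported SE / correct SE = r = √(1 + d²/4).

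In a balanced 2×2 the adjusted and unadjusted mean differences are the same number. The estimate itself is therefore no more variable; only its reported SE is too large. Hence:

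- actual two-sided type I error = 2 × [1 − Φ(1.96 r)]
- power, where the correct SE would give 80% = Φ(1.96 + 0.842 − 1.96 r)

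| d (assumed) | r | SE too large by | Type I error | Power |
|---|---|---|---|---|
| 0 | 1.000 | 0% | 5.0% | 80.0% |
| 0.3 | 1.011 | 1.1% | 4.7% | 79.4% |
| 0.5 | 1.031 | 3.1% | 4.3% | 78.3% |
| 0.8 | 1.077 | 7.7% | 3.5% | 75.5% |

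Simulation with 50 per cell agrees: null rejection was 4.6%, 4.3% and 3.5% for d = 0.3, 0.5 and 0.8. At d = 0.8 the empirical SD of the estimate was 0.141 against a mean reported SE of 0.152.

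**3. Log-rank test**

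Simulation of 4,000 runs, 40 per cell, no censoring, hazard ratio 1.5 for the tested factor:

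| Other factor's hazard ratio | Power, unstratified | Power, stratified |
|---|---|---|
| 1.0 | 72% | 71% |
| 1.5 | 68% | 70% |
| 2.0 | 64% | 70% |

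Stratifying costs almost nothing when the other factor is inert and helps when it is not.

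**4. Precision of an interaction estimate (pulmonary complications)**

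With total N and a common risk p:

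- SE of a main risk difference = √(4p(1−p)/N)
- SE of the difference in risk differences = √(16p(1−p)/N), which is twice as large

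| N | p | 95% half-width, main effect | 95% half-width, interaction |
|---|---|---|---|
| 100 | 30% | 1.96 × √(0.84/100) = 18.0 points | 35.9 points |
| 200 | 20% | 1.96 × √(0.64/200) = 11.1 points | 22.2 points |
| 400 | 10% | 1.96 × √(0.36/400) = 5.9 points | 11.8 points |

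If N gave 80% power for a main effect, power for an interaction of the same size would be about 29%.

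**5. Why the scale must be named**

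Assume risks of 30% with neither monitor and 20% with either alone.

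- No interaction on the odds-ratio scale: odds with both = 0.25²/0.4286 = 0.1458, a risk of 12.7%. The risk difference then goes from −10.0 to −7.3 points.
- No interaction on the risk-difference scale: risk with both = 10%. The odds ratios are 0.583 without and 0.444 with the other monitor, a ratio of 0.76.

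The same data can show an interaction on one scale and none on the other.

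**The case against.** The strongest reply is that the plan is already sound for its aims. The Introduction states two separate aims, and a marginal comparison is a standard, valid primary analysis of a factorial trial. This stands. A reader might infer that the two-group tests are biased or inflate type I error. They do not: the other factor is randomised independently of outcome, and step 2 shows that the test errs, if at all, on the conservative side.

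Second, the multivariable logistic and Cox models could include the other factor. This stands in part. It would be too strong to say that the plan excludes the other factor; it is left unspecified. But those models are described as a search for influential factors, not as the estimate of the treatment effect.

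Third, stratified randomisation may mean that one factor is balanced within the other. That is a possible reading, but the strata are unnamed, and balance at allocation does not put the factor into the analysis.

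Fourth, the case for an interaction is thin. The Background says: "The hemodynamic instability may further increase the risk of inadequate depth of anesthesia and thereafter its related complications". A reader might take this as evidence of an interaction on the primary outcomes. The sentence goes on to awareness, post-traumatic stress and cognitive dysfunction, not to eye opening or pulmonary complications. The shared role of mean arterial pressure makes an interaction possible, but the documents show no direct pathway to either primary outcome.

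Fifth, the interaction estimate could rule out only large interactions. That is correct. It is a reason to label it exploratory and show the interval, not a reason to omit it.

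**Conclusion.** The point holds as a gap in specification. The plan does not commit to using the other randomised factor in either primary comparison, and it would not display the four groups or the interaction.

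The size is modest. Under balanced cells and a continuous outcome, intervals are 0% to 7.7% too wide for an assumed shift of 0 to 0.8 SD, and power falls from 80% to between 79.4% and 75.5% for shifts of 0.3 to 0.8 SD. If the other monitor has no effect on the outcome, nothing is lost in precision. The documents support no particular value of the shift.

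The gain in interpretation is also limited: over the assumed N of 100 to 400 and risks of 10% to 30%, the interaction half-widths calculated run from about 12 to 36 percentage points. The documents do not support a claim that the averaged effects are invalid or that an interaction is likely. The change is still worth making, because it uses groups that the trial already randomises, and because naming the model and scale in advance removes a choice after the results are seen.

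**What to change.** Amend the Statistical Analysis section as follows.

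1. Estimate each primary effect with its 95% CI, stratified by or adjusted for the other randomised factor and any stratification variable actually used.
   - Pulmonary complications: a Mantel-Haenszel test and common risk difference.
   - Time to eye opening: a log-rank test stratified by the other factor, plus a named effect estimate such as a stratified Cox hazard ratio, since the log-rank test alone gives no estimate.
   - State that adjusted odds or hazard ratios are conditional and generally differ from the marginal ones.
   - Where linear regression is used for a treatment effect, include both factors.
2. Tabulate each primary outcome in all four cells.
3. Report the M-Entropy × ProAQT interaction with its 95% CI on a named scale (for complications, the difference in risk differences). Label it exploratory and low in precision, and do not use it as a gate for the main analyses.

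The cost is SAP wording, a few lines of SAS and one table. No extra patients or data are needed.

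### One unadjusted 0.05 level covers every outcome, so any of 13 to 15 secondary results, delirium among them, could be called statistically significant

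*Combined protocol and SAP*

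**What the plan says.** All references are to the combined protocol and SAP.

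- **Statistical Analysis.** The scope is stated generally: "The distributions of baseline patient characteristics and outcome variables will be compared between two groups". The level is then set once: "A two-sided significance level of 0.05 was used to define statistically significant difference". Categorical outcomes are compared "using chi-square tests or Fisher's exact test for categorical variables". The section says nothing on multiplicity, testing order or the standing of secondary results, and no other section does.
- **5. Study Methods, M-Entropy study.** The one primary outcome is time to spontaneous eye opening. The secondaries are three times ("Secondary outcomes include time to tracheal extubation, time to orientation in time and place, time to leave operating room") and three kinds of event ("events of emergence agitation, postoperative delirium, and intraoperative recall or awareness").
- **5. Study Methods, ProAQT study.** The one primary outcome is in-hospital pulmonary complication, a composite. The secondaries are the relative change of PaO2/FiO2, its "values after induction of anesthesia and at the end of surgery, acute kidney injury", cardiac complications (infarction and new atrial fibrillation), hypotensive episodes, stroke and length of stay. The subsection adds: "All outcomes will be determined again 30 days after surgery and documented by research staff blinded to group allocation".
- **1. Introduction.** Aim 1 reads: "To evaluate the effect of M-Entropy guidance on the emergence from anesthesia and risk of postoperative delirium".

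**The concern.** The plan names one primary outcome per factor, but its only rule about significance does not use that distinction. A secondary result with p = 0.04 gets the same label as a primary result with p = 0.04.

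Delirium is where this matters most. Aim 1 names it next to emergence, while the outcome list makes it one of six secondaries. Suppose eye opening shows no difference and delirium gives p = 0.04. The plan does not say whether that meets aim 1 or only suggests a hypothesis. If this is settled after the data are seen, the reported error rate loses its meaning.

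**Working it through.** The plan states no familywise error rate, so there is no figure of its own to reproduce. The text available gives no arm size, event rate or correlation either. All such values below are assumptions.

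**1. Count of secondary outcomes**

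- M-Entropy: 3 times + 3 events = 6.
- ProAQT: PaO2/FiO2 counts as 2 or 3, acute kidney injury 1, cardiac 1 or 2, hypotension 1, stroke 1, stay 1. The total is 7 to 9.
- Both: 13 to 15. Fifteen requires counting the two PaO2/FiO2 time points and the two cardiac events separately.

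**2. Chance of at least one p < 0.05, all nulls true, independent tests at full 5% size**

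Formula: 1 − 0.95^m.

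| Family | m | Result |
|---|---|---|
| M-Entropy | 6 | 1 − 0.7351 = 26.5% |
| ProAQT | 7 | 1 − 0.6983 = 30.2% |
| ProAQT | 9 | 1 − 0.6302 = 37.0% |
| Pooled | 13 | 1 − 0.5133 = 48.7% |
| Pooled | 15 | 1 − 0.4633 = 53.7% |

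For two-sided tests with jointly normal statistics, dependence can only lower these values (Šidák's inequality). They are therefore ceilings for the listed outcomes.

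**3. Equal correlation between all test statistics** (simulation, 200,000 draws; pooled, 13 to 15 tests)

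| Assumed correlation | Result |
|---|---|
| 0.3 | 42% to 46% |
| 0.5 | 33% to 36% |
| 0.7 | 24% to 26% |

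Using one correlation across both factors is a simplification.

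**4. A scenario closer to these outcomes**

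Assumptions:
- The three recovery times are correlated at 0.7.
- The two PaO2/FiO2 values are correlated at 0.5, and the relative change is treated as their standardised difference.
- Length of stay and the events are independent of the rest.
- Events are tested with Fisher's test at these rates: agitation and hypotension 20%, delirium 10%, kidney injury and atrial fibrillation 5%, infarction 1%, stroke and recall 0.5%.

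| Assumed patients per arm | M-Entropy | ProAQT | Both |
|---|---|---|---|
| 50 | 15.0% | 20.1% | 32.1% |
| 100 | 16.4% | 22.8% | 35.4% |
| 150 | 16.9% | 23.7% | 36.6% |

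Check of the first row: 1 − (1 − 0.150)(1 − 0.201) = 0.321. The true size of Fisher's test at event rates of 0.5% to 1% is 0 to 0.2%, so the rarest events add almost nothing.

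**5. Direction**

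These figures count chance results either way. For a chance result favouring the intervention, under independence, the formula is 1 − 0.975^m:

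- M-Entropy (6): 14%.
- ProAQT (7 to 9): 16% to 20%.
- Pooled (13 to 15): 28% to 32%.

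**6. Aim 1**

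If aim 1 could be claimed on either eye opening or delirium, each at 0.05, the ceiling is 1 − 0.95² = 9.75%. Testing delirium only after eye opening is significant returns it to 5%.

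**The case against.** The strongest reply has four parts.

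- **A hierarchy exists.** Each study names one primary outcome and labels the rest secondary, and unadjusted secondary analyses are common. A reader might infer that the plan lets a chance secondary replace a null primary. It does not say so: it defines a label for a p-value and sets no rule for trial success. What stands is that this label is identical for primary and secondary outcomes.
- **The size is easily overstated.** A reader might infer that a false positive is about as likely as not. That needs 13 to 15 independent tests, each at its full 5% size, pooled over two comparisons that section 4 (Study Design) describes as two studies in one patient group. Recovery times are successive steps of one process, and the change in PaO2/FiO2 appears to be derived from the two values also listed. The value after induction precedes most of the intervention, so it is a weak basis for a benefit claim. This objection stands: the per-factor figures should lead.
- **Delirium is not ranked with the primary.** A reader might infer equal rank from aim 1. The aim assigns neither rank nor alpha, and the outcome list says secondary. What stands is that the plan does not say how a delirium result bears on the aim.
- **The 30-day assessment is not a second set of tests.** A reader might double the count. The text says outcomes are determined again, not tested again. The intraoperative PaO2/FiO2 values cannot recur, and cumulative events would correlate strongly with the in-hospital result. No figure here includes it.

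**Conclusion.** The concern holds for secondary claims only. As written, the plan would attach the label of statistical significance to any of 13 to 15 secondary results without protection. With every null true, the chance of at least one is at most 26% for M-Entropy and 30% to 37% for ProAQT. Under the dependence, event rates and arm sizes assumed above it is about 15% to 17% and 20% to 24%. Even the lowest of these is about three times 5%. About half of such results would favour control.

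Testing each factor's own primary outcome at 0.05 is sound and is not questioned. The documents do not support an even chance of a false claim as the headline, because that figure is the top of the pooled range.

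**What to change.** Replace the single sentence on the significance level with a short paragraph stating that:

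1. the two-sided 0.05 significance claim applies to the one primary outcome of each factor;
2. secondary results, and any 30-day results, are reported as estimates with 95% confidence intervals and labelled exploratory;
3. if a delirium claim is wanted for aim 1, delirium is tested at 0.05 only after the M-Entropy primary is significant.

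An adjustment within each factor would also close the gap. Bonferroni gives 0.05/6 = 0.0083 for M-Entropy and 0.05/9 = 0.0056 for nine ProAQT outcomes. It is the stricter route for any one outcome.

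The change should be made before unblinded results are seen. It needs no extra patients, no change in conduct and no power from either primary test. The price is that secondary findings can no longer be announced as statistically significant, and delirium cannot be claimed if eye opening shows no significant difference.
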